#### Part 2 (CHICO SECURE)

No imputations will be made for missing data due to dropouts or other causes. For the primary efficacy analysis done on the FAS, drop-outs will be included in the analysis using a Poisson distribution with person-year.

## 4.4 Interim Analyses and Data Monitoring

No interim analysis is planned.

## Part 1 (CHICO)

An independent Data Monitoring Committee (DMC) will meet periodically to review the safety data of enrolled subjects, as well as the continuing scientific merit of the trial.

The DMC may recommend stopping enrollment in the case of a negative risk/benefit assessment. The DMC will be comprised of a minimum of two clinicians with expertise in relevant clinical specialties and at least one statistician knowledgeable about statistical methods for clinical trials. Each committee member will be screened for evidence of an absence of serious conflicts of interest. The operation of the DMC will be governed by a charter that will describe the group's frequency of meetings, procedures (including, but not limited to, periodic safety monitoring), and requirements for reporting its observations to the Sponsor.

#### Part 2 (CHICO SECURE)

No DMC is planned.

BAY No. A2502/IMPACT No. 16027

Page:

## 4.5 Data Rules

#### Baseline

Baseline is defined as the last measurements performed prior to the first study drug administration, which is either in Visit 1 (e.g. parameters of serum hematology, chemistry, coagulation, and urinalysis) or Visit 2 (e.g. vital signs and ECG), unless otherwise specified. If Visit 2 is missing, use data from Visit 1 instead.

#### **Repeated measures**

If there are repeated measurements per time point (e.g. laboratory values, vital signs, etc.), the following rules will be used:

• Before the start of the study drug administration (i.e., for screening and baseline value), the latest measurement will be used, in the event these latest measurements are measurements at scheduled visits. Unscheduled visits will be used, if there are no measurements at scheduled visits. If the latter is the case, the last unscheduled visit will be used.

• In case of repeated measurements at any post-screening time point, the first value of the scheduled measurements at that time point will be used. No unscheduled measurements will be used for any time points beside screening / baseline even where measurements at scheduled visits are missing.

In case of non-adherence to time windows, data will be assigned to the nearest nominal visit according to assessment schedule.

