9.2.3.2 Visit 10 (Day 240 ± 7)

- Assessment of Chagas' disease signs and symptoms (to be performed during physical examinations); see Section 9.4.4
- 12-lead ECG (optional in subjects < 5 years of age at the discretion of the investigator)¹³⁷
- Conventional and non-conventional serologic testing for Chagas' disease and qPCR¹³⁸
- Assessment of AEs
- Concomitant medications
- Brief physical examination, including assessments of heart, lungs, and abdomen, skin for the presence of severe dermatitis, and clinical assessments for the presence of peripheral neuropathy. Abnormal findings will be documented as AEs (see Section 9.6.1.1).
- Vital signs (blood pressure is optional in subjects < 5 years of age at the discretion of the investigator), height/length, and weight¹³⁹

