9.2.3.3 Visit 11 (Day 420 ± 7)

- Assessment of Chagas' disease signs and symptoms (to be performed during physical examinations); see Section 9.4.4
- 12-lead ECG (optional in subjects < 5 years of age at the discretion of the investigator)¹⁴⁰
- Conventional and non-conventional serologic testing and IHA for Chagas' disease and qPCR ^{141,142}
- Assessment of AEs
- Concomitant medications

¹³⁶ Text added/deleted/modified for clarity and to reflect changes made per Amendment 1

¹³⁷ Modified as per amendment 2.

¹³⁸ Modified as per amendment 2.

¹³⁹ Text added/deleted/modified for clarity and to reflect changes made per Amendment 1

¹⁴⁰ Modified as per amendment 2

¹⁴¹ IFA test added per amendment 5.

¹⁴² Replaced IFA with IHA per Amendment 6.

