9.4.2 Serological tests

At screening, subjects must have the following serological tests to confirm a diagnosis of Chagas' disease:

- Subjects < 8 months of age at randomization must demonstrate direct observation of *T. cruzi* by concentration test¹⁴⁹
- Subjects ≥ 8 months to < 18 years of age at randomization must demonstrate a positive conventional ELISA result for both of the following tests to confirm diagnosis:
 - Recombinant ELISA
 - Total purified antigen ELISA¹⁵⁰

Additionally, a non-conventional ELISA test and IHA will be obtained; however, a positive result will not be required for diagnosis^{151,152}.

Subjects will also be eligible if there is acceptable documentation of positive Chagas' disease within 3 months prior to screening and they have had no prior anti-trypanocidal or anti-parasitic treatment.¹⁵³

After randomization, conventional and non-conventional serological tests will be performed at Visits 3, 6, and 8 (EOT), and Visits 10 and 11 (Follow-up).¹⁵⁴

All subjects ≥ 8 months to < 18 years of age at randomization will have two baseline specimens collected for serologic testing. One sample will be used to determine the initial diagnosis of Chagas' disease while the other sample will be frozen and retained to be assayed later as an internal control. Subjects < 8 months of age at randomization will have one specimen obtained, which will be frozen and retained. Total blood volume to be taken for the

¹⁴⁸ Modified as per amendment 2

¹⁴⁹ Text modified for clarity (Amendment 1)

¹⁵⁰ Text modified for clarity and per Modification 2 (Amendment 1)

¹⁵¹ IFA test added per Amendment 5.

¹⁵² Replaced IFA with IHA per Amendment 6.

¹⁵³ Text modified/added for clarity and per Modification 2 (Amendment 1)

¹⁵⁴ Text modified for clarity and to reflect changes per Amendment 1

	Integrated Clinical Study Protocol BAY A2502/ 16027
03 NOV 2020	Version 11.0

required three serological and PCR tests is 4.0-5.0 mL, depending on the subject's age. Care will be taken to minimize sample volumes by using a micro-sampling collection technique, when possible.¹⁵⁵

Page: 63 of 259

Details describing the collection, processing, storage and shipment of blood samples, and the serologic test protocols, will be described in a separate serologic test manual from the central laboratory.

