#### Primary variable(s)

The primary efficacy variable will be sero-reduction or sero-conversion at 12 months posttreatment using two conventional ELISA serology tests as the measure of efficacy.

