## **3.2** Part 2 (CHICO SECURE)

#### **Design overview**

This is a prospective, long-term follow-up of subjects, who were randomized and received at least one dose of their assigned 60- or 30-day nifurtimox treatment. The study is designed to evaluate seronegative conversion and serial reduction in OD measured by ELISA.

Subjects will be followed up for a total of 4 years after end of nifurtimox treatment. The first year of follow-up period is included in part 1 and 3 years of follow-up are included in part 2 of the study.

The following age categories will be considered for part 2 of the study:  $\leq 2$  years,  $\geq 2$  years to  $\leq 6$  years,  $\geq 6$  to  $\leq 12$  years,  $\geq 12$  to  $\leq 18$  years (age is defined as subject's age at randomization).

Subjects enrolled will be followed annually with visits to the investigational site. Seronegative conversion will be measured by two types of assay, recombinant ELISA and IHA. For assessment of serial reduction compared to baseline defined as screening visit of part 1 (Visit 1), OD will be measured by recombinant ELISA and total purified antigen ELISA.

The first visit should be performed as soon as possible after availability of regulatory and ethics committee approval for all subjects who have already completed part 1 of the study for 1 year  $\pm$  6 weeks or longer. Subjects who are entering the study beyond the time window for FU Visit 1 (2 years  $\pm$  6 weeks) will have their eligibility assessments as soon as possible provided that consents/assents have been obtained. Subjects will have annual visits at the investigational site for efficacy and safety assessments for 3 years. Timing of study visits is relative to end of treatment in part 1 of the study.

Between the annual visits at the investigational site, subjects and/or his or her parent(s) or legally authorized representative(s) will be contacted by qualified personnel by a method agreed (eg. phone call) about 6 months after a visit at the investigational site to identify the occurrence of potential clinical symptoms of Chagas' disease or any pathology mentioned in the exclusion criteria using a structured interview. In case of suspected findings, an unscheduled visit at the investigational site to initiate appropriate diagnostic evaluations will be requested.

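### SAP 4.5 does not protect the on-target serology sample: nearest-visit assignment plus a first-value rule can put an earlier sample in the 12-month or annual slot

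*SAP*

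**What the plan says.** SAP 4.5 (Data Rules, under Repeated measures) holds three rules that matter here. For several values at one time point after screening: "In case of repeated measurements at any post-screening time point, the first value of the scheduled measurements at that time point will be used". For unscheduled values: "No unscheduled measurements will be used for any time points beside screening / baseline even where measurements at scheduled visits are missing". For late or early visits: "In case of non-adherence to time windows, data will be assigned to the nearest nominal visit according to assessment schedule". No outer limit is set on the re-assignment, the order of the rules is not stated, and there is no preference for the value nearest the target day or for the value labelled with that visit.

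SAP 3.1 sets the Part 1 endpoint: "The primary efficacy variable will be sero-reduction or sero-conversion at 12 months posttreatment using two conventional ELISA serology tests as the measure of efficacy". SAP 6.2.1.1 defines cure and handles discordant or missing ELISA results, but adds no window or selection rule for the 12-month serology. Protocol 9.4.2 schedules serology after end of treatment (EOT) in Part 1 only at Visits 10 and 11.

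For Part 2, SAP 3.2 foresees late entry: "Subjects who are entering the study beyond the time window for FU Visit 1" (2 years ± 6 weeks) are assessed as soon as possible. SAP 6.2.2.1 counts conversions over the four years, divides by a person-time sum built from the number at risk at each annual visit (N_i × V_i), and also reports conversion by visit.

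**The concern.** Once out-of-window samples have been assigned to visits, two scheduled samples can share one slot. Keeping the first of them then retains the earlier sample, which is the one further from the target day when the later sample was taken on time.

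In Part 1 a very late Visit 10 sample could stand in for the Day 420 sample on which the primary endpoint is meant to rest. In Part 2 a late FU Visit 1 sample could take the Year 3 slot, and a late FU Visit 3 sample the Year 4 slot.

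The direction is fairly clear. Protocol section 3 says seronegative conversion can take years to decades. The benznidazole study described in Protocol 5.1 shows mean antibody reductions of 21% at 12 months, then 23%, 29% and 27% at 18, 24 and 48 months. An earlier sample would therefore tend to be read as no cure or not converted. Discarding an on-time result for an off-time one is hard to defend even when the bias is conservative.

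**Working it through.** **Inputs.** EOT is Day 60, Visit 10 is Day 240 ± 7 and Visit 11 is Day 420 ± 7 (Protocol Table 9–1). FU Visits 1, 3 and 5 are at Years 2, 3 and 4, each ± 6 weeks (Protocol Table 9–2). The 60-day arm has n = 200, assumed cure 55%, goal 16% and stated power 99% (Protocol 10.4). The interval formula is in SAP 6.2.1.1 and the 45% benznidazole threshold in SAP 6.2.1.3.

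**1. The plan's own figure.** With p = x/n, the lower limit is L = p − 1.96·√(p(1 − p)/n) − 1/(2n). At n = 200:
- x = 43: 0.2150 − 0.0569 − 0.0025 = 0.1556, which fails.
- x = 44: 0.2200 − 0.0574 − 0.0025 = 0.1601, which passes.

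So at least 44 cures are needed. Exact binomial power at 55% is above 99.99%, consistent with the stated 99%.

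**2. Part 1 boundary.** (240 + 420)/2 = Day 330. A Visit 10 sample moves only if drawn after Day 330. That is more than 330 − 240 = 90 days after its nominal day and more than 330 − 247 = 83 days past its window. At Day 331 it is 331 − 60 = 271 days after EOT, about 9 months, against the intended 360.

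**3. Part 2 boundaries.** (2 + 3)/2 = 2.5 years and (3 + 4)/2 = 3.5 years. Half a year is about 26 weeks, so a colliding visit is about 26 − 6 = 20 weeks past its window. This assumes that only visits with scheduled serology count as nominal visits. If the phone contacts at Years 2.5 and 3.5 also counted, displacement would begin at 2.75 and 3.75 years.

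**4. Effect on the 16% test.** One displaced child moves the 60-day rate by at most 1/200 = 0.5 points and the 30-day rate by at most 1/100 = 1.0 point. Expected cures are 0.55 × 200 = 110, so 110 − 44 + 1 = 67 must be lost before superiority fails. The documents do not say how many children would be affected. As an assumed range, let a share f be displaced with none of them cured, so the rate is 0.55(1 − f):

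| f | Cure rate | Lower limit |
|---|---|---|
| 1% | 54.5% | 47.3% |
| 5% | 52.3% | 45.1% |
| 10% | 49.5% | 42.3% |
| 20% | 44.0% | 36.9% |

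All stay far above 16%.

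**5. Effect on the 45% benznidazole rule.**
- x = 110: 0.5500 − 0.0689 − 0.0025 = 0.4786
- x = 105: 0.5250 − 0.0692 − 0.0025 = 0.4533
- x = 104: 0.5200 − 0.0692 − 0.0025 = 0.4483

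At least 105 cures are needed, so losing 110 − 105 + 1 = 6 of the 110 reverses the conclusion.

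**6. Part 2 scale.** SAP 6.5 assumes 5% of 170 children convert, or 8.5 events. If one conversion were missed, the count would fall by 1/8.5, about 12%.

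**The case against.** The best defence is that the SAP never says the rules run in sequence. The repeat rule is printed before the window rule, its examples are laboratory values and vital signs, and its reference to measurements scheduled at that time point can be read as admitting only the Visit 11 draw. On that reading nothing is displaced. SAP 4.6 also offers a validity review in which odd cases can be settled and documented.

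Part of this stands: displacement is a possible result of unclear wording, not a stated rule. But repeated values at a time point can be recognised only after values have been assigned to time points. The SAP contrasts scheduled with unscheduled measurements, and a Visit 10 draw is scheduled. If the protective reading is intended, it needs to be written down. Leaving it to the validity review means choosing between two available results after the fact.

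Four stronger readings are tempting but unsupported:
- **Any late Visit 10 sample displaces the 12-month one.** It does not; samples from Day 248 to Day 329 are late but stay at Visit 10.
- **An early stopper's EOT sample is re-labelled as Day 30.** The window rule is triggered by non-adherence, and Protocol 5.1 and SAP 4.2 themselves set that sample at 30 ± 3 days after the last dose. It follows its own timing.
- **The COVID-19 summaries in SAP 6.1.1 show that such cases are expected.** They cover discontinuations and deviations in general and say nothing about out-of-window serology.
- **A Part 2 conversion is lost outright.** SAP 6.2.2.1 counts conversions over the whole period. Nothing says that an observed one is dropped because two visits share a label, so an effect on the count is an inference.

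**Conclusion.** The gap is real and worth closing, but modest. SAP 4.5 permits a reading under which an on-time Day 420 or annual sample is set aside for an earlier one, and no other section prevents it.

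In Part 1 this needs a Visit 10 sample drawn after Day 330 from a child who also attends Visit 11, which is probably rare. In Part 2 late entry is foreseen, so collisions are more plausible. The by-visit results would be affected directly, and the person-time sum and conversion count possibly, depending on how they are programmed.

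The bias runs toward no cure or not converted. The 16% superiority conclusion is very unlikely to change, since 67 of 110 expected cures would have to be lost. The exploratory 45% comparison has less room, with a margin of 6 cures. These margins assume n = 200 and 55% cure. The number of affected children is unknown, and the range shown is an assumption with the worst outcome for every displaced child.

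**What to change.** In SAP 4.5, for post-baseline efficacy serology only, replace the first-value rule with a ranked one that also takes precedence over nearest-visit assignment:

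1. Use the sample collected at the visit labelled Visit 11 (or the relevant FU visit) if there is one.
2. Otherwise use the scheduled sample closest to the target day: Day 420 for Visit 11, the anniversary of EOT in Part 2.

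The ranking matters because the two criteria can disagree. With Visit 10 drawn on Day 415 and Visit 11 on Day 430, the label picks Day 430 and proximity picks Day 415.

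State that visit assignment comes before repeat selection. For Part 2, state that a conversion seen at any scheduled sample counts. It would also help to say whether the fallback in step 2 has an outer limit, since without one a Day 331 sample could still serve as the 12-month value when Visit 11 was missed.

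The cost is a short SAP amendment and changes to the visit-selection and Part 2 conversion derivations. No new data are needed, and few children's values should change.

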9.2.2.3 Visit 4 (Day 14 ± 1 days)

Study site personnel will contact the subject/legally authorized representative via telephone to assess for the occurrence of AEs, use of concomitant medications, compliance with study drug administration, and completion of subject diary or PK subject diary¹²⁶. A Phone Contact Form for the telephone contacts to obtain safety and compliance information will be provided to all sites (Section 16.1). If any safety concern arises, subjects may return to the study site for an Unscheduled Visit.¹²⁷

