9.6.3 Further safety

9.6.3.1 Laboratory assessments

Safety laboratory assessments will be performed at screening, Visits 3, 6, 8 (EOT), and 9 (follow-up). Fasting is dependent on the age of the subject at the discretion of the investigator. If any abnormal laboratory values occur at the EOT Visit (Visit 8), these determinations will be followed until normal or stable.¹⁶⁹

Laboratory parameters will be analyzed by a local laboratory according to the schedule specified in Table 9–4: .

¹⁶⁸ Sentence corrected as per amendment 3

¹⁶⁹ Heading 9.6.3.1 added; text modified for clarity and to reflect changes made per Amendment 1.

|--|

Table 9–4:	Description	of laboratory	parameters	(safety)
------------	-------------	---------------	------------	----------

Hematology	Hemoglobin, hematocrit, RBC count, WBC count and differential (including lymphocytes, monocytes, eosinophils, basophils, neutrophils), MCV, MCH, MCHC, platelets
Blood chemistry	Albumin, total protein, BUN, creatinine, glucose, total bilirubin, ALP, AST, ALT, uric acid
Coagulation	INR, PT, PTT
Urinalysis (urine dipstick) a	RBCs, WBCs, pH, specific gravity, glucose, protein, bilirubin, urobilinogen, nitrite, ketones
Urine pregnancy test ^b	Urine β-hCG

Page: 74 of 259

ALP = alkaline phosphatase, ALT = alanine aminotransferase, AST = aspartate aminotransferase, β-hCG = beta-human chorionic gonadotropin, BUN = blood urea nitrogen, INR = international normalized ratio, MCV = mean corpuscular volume, MCH = mean corpuscular hemoglobin, MCHC = mean corpuscular hemoglobin concentration, PT = prothrombin time, PTT = partial thromboplastin time, RBC = red blood cell, WBC = white blood cell.

 a If abnormalities are identified by the dipstick, the samples will be sent for confirmatory testing¹⁷⁰. Cell/sediment microscopy should be performed only if positive dipstick results are obtained for WBC, RBC/hemoglobin, or protein.

b To be performed at Visits 1, 2, 3, 6, 8, and 9 on females of childbearing potential (i.e., female subjects who have experienced menarche). If any urine pregnancy test is positive, a serum pregnancy test will be performed to confirm the result.¹⁷¹

Safety laboratory assessments are not applicable in part 2 of the study.

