## Laboratory Data

Quantitative data will be summarized by means of descriptive statistics (arithmetic mean, standard deviation, median, minimum and maximum) by visit and treatment regimen for the original data as well as for the difference to baseline. Frequency tables will be provided for qualitative data. Summaries will be given by treatment regimen. The incidence of laboratory data outside the reference range (low, high) and clinically significant laboratory changes will be summarized by treatment regimen using frequency tables. The definitions of incidence are as follows:

- Incidence of high lab abnormalities: # of subjects with at least one high laboratory assessment after the start of treatment who had a normal or lower than normal laboratory assessment at baseline / # of subjects at baseline with a normal or lower than normal laboratory assessment who also had at least one valid laboratory value after start of treatment. Subjects with missing or high abnormal values at baseline are not included in the denominator.
- Incidence of low lab abnormalities: # of subjects with at least one low laboratory assessment after the start of treatment who had a normal or higher than normal

laboratory assessment at baseline / # of subjects at baseline with a normal or higher than normal laboratory assessment who also had at least one valid laboratory value after start of treatment. Subjects with missing or low abnormal values at baseline are not included in the denominator.

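### SAP 4.5 bars unscheduled post-baseline laboratory values, SAP 6.3 counts any abnormal value after treatment starts, and nothing says which governs the Part 1 abnormality tables

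*SAP*

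**What the plan says.** SAP 4.5 (Repeated measures) opens with its scope: "If there are repeated measurements per time point (e.g. laboratory values, vital signs, etc.), the following rules will be used". Before the first dose, an unscheduled value may stand in where no scheduled value exists. After that, the first scheduled value represents each time point, and "No unscheduled measurements will be used for any time points beside screening / baseline even where measurements at scheduled visits are missing".

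SAP 6.3 (Laboratory Data) plans two kinds of laboratory output:

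- Quantitative results are summarised "by visit and treatment regimen for the original data as well as for the difference to baseline".
- The incidence of abnormalities is counted per child. The numerator for high values is the number "of subjects with at least one high laboratory assessment after the start of treatment", and for low values the number "of subjects with at least one low laboratory assessment after the start of treatment", among children not already abnormal in that direction at baseline. The denominator is restricted to those "who also had at least one valid laboratory value after start of treatment". Clinically significant changes are also to be tabulated.

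The incidence definitions name no visit and do not mention scheduled or unscheduled samples.

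In the protocol, post-baseline safety laboratory tests fall at Visits 3, 6, 8 and 9 (section 9.6.3.1), that is Days 7, 30, 60 and 90 in Table 9-1. The contacts at Days 14, 21 and 42 are telephone calls, for which section 9.2.2.3 and its counterparts for Visits 5 and 7 add: "If any safety concern arises, subjects may return to the study site for an Unscheduled Visit".

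**The concern.** A rule that picks one value per nominal visit suits by-visit means. Carried over to a count of children with any abnormal value, it removes results drawn because someone was worried about the child. The final clause of the 4.5 rule goes further than choosing between duplicates, since it excludes an unscheduled value even when there is no scheduled value to prefer. It sits among the general statistical considerations with no exception for safety tables, so a programmer could reasonably apply it to the incidence tables.

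The scheduled tests are sparse where this matters. Between Day 7 and Day 30, and between Day 30 and Day 60, no laboratory test is scheduled. Days 31 to 60 are the only period in which the two regimens differ in treatment, and the next scheduled sample after Day 30 is at Day 60. Laboratory tolerability is part of a secondary objective (Protocol 4.1). Severe hepatic impairment and severe leukopenia are among the situations in which a child may be withdrawn (Protocol 6.3.1).

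**Working it through.** The plan states no figure on this point, so there is nothing to reproduce. The check compares the two rules and then asks what follows if 4.5 governs.

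**Which values enter each table**

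| Table | SAP 4.5 applied throughout | SAP 6.3 definition read alone |
|---|---|---|
| By-visit summaries | first scheduled value per time point | consistent with 4.5 |
| High/low incidence, numerator | abnormal on a scheduled sample | abnormal on any sample after treatment starts |
| High/low incidence, denominator | at least one scheduled post-baseline value | at least one valid post-baseline value of any kind |

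The two readings give the same by-visit tables and different incidence tables. Neither section refers to the other.

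**Effect if 4.5 governs**

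Let N be the children in the denominator and X those abnormal when all values count. Let b be children with a scheduled post-baseline value who are abnormal only on an unscheduled sample. Let m be children with no scheduled post-baseline value, of whom a are abnormal.

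- All values: X / N
- Scheduled values only: (X − b − a) / (N − m)

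*Case 1: every child has a scheduled post-baseline value (m = a = 0).* The rate becomes I × (1 − s), where I = X / N and s = b / X. It cannot rise. The planned 60-day arm of 200 (Protocol 10.4) is used for N. I and s are assumptions, because the documents give neither.

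| I | s = 0 | s = 10% | s = 25% | s = 50% |
|---|---|---|---|---|
| 5% | 5.0% | 4.5% | 3.75% | 2.5% |
| 10% | 10.0% | 9.0% | 7.5% | 5.0% |
| 20% | 20.0% | 18.0% | 15.0% | 10.0% |

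At I = 10%, the children lost from the numerator are 200 × 0.10 × s, that is 0, 2, 5 and 10.

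*Case 2: some children have only unscheduled values.* Start from 20/200 = 10.0%, with m = 10 and b = 0:

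- a = 0: 20/190 = 10.5%
- a = 1: 19/190 = 10.0%
- a = 5: 15/190 = 7.9%

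In general the reported rate rises only when N(a + b) < mX, that is when (a + b)/m is below X/N. This needs m > 0, so a reversal can come only through children with no scheduled post-baseline value of that parameter.

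**The case against.** The best defence is scope. The 4.5 rule is introduced as a way to choose one value per time point, and the incidence in 6.3 is not a time-point statistic. On that reading 6.3 already counts unscheduled values and nothing is lost. This is a fair reading, and it is why understatement cannot be asserted as a fact. It does not settle the matter, because 4.5 names laboratory values, applies even when the scheduled value is missing, and is nowhere switched off for the incidence tables.

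A second defence is that abnormal laboratory findings can be adverse events (Protocol 9.6.1.1), and SAP 6.3 reports all adverse events whatever the visit. A marked abnormality should therefore appear there. That stands as mitigation, but it depends on investigator reporting and does not correct the laboratory tables. Return for an unscheduled visit is also optional, and no laboratory panel is specified for it in Part 1, so the number of children affected may be small.

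Three stronger readings are tempting and are not supported:

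- *The visit gaps give the size of the loss.* If onset is uniform over Days 1 to 60, a scheduled test at the nominal days misses a 7-day abnormality for 39 of 60 onset days (65%), a 14-day one for 25 of 60 (42%) and a 21-day one for 11 of 60 (18%). These figures describe the visit schedule. Without an unscheduled sample, the abnormality goes unseen under any SAP rule. Only children sampled at an unscheduled visit and abnormal nowhere else are affected.
- *The repeats of end-of-treatment tests are lost cases.* The protocol says: "If any abnormal laboratory values occur at the EOT Visit (Visit 8), these determinations will be followed until normal or stable". Those children already have an abnormal scheduled value, so omitting the repeats does not change the high/low count.
- *The error can go only one way.* Case 2 in the working shows that it can reverse when children leave the denominator.

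**Conclusion.** The inconsistency is real and should be resolved. SAP 4.5 as written excludes unscheduled post-baseline laboratory values. SAP 6.3 defines an incidence that does not exclude them, and the SAP does not say which prevails. If 4.5 governs, the Part 1 rates of high and low abnormalities would tend to be understated. Among children with at least one scheduled post-baseline value the effect can only be downward.

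The size rests on s, the share of abnormal children whose only abnormal value is unscheduled, and the documents give no basis for it. The tabulated range is therefore illustrative.

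The point is confined to Part 1, since Part 2 has no safety laboratory tests (Protocol 9.6.3.1). All Part 1 safety analyses are descriptive (SAP 6.3), and the efficacy conclusions do not depend on it.

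**What to change.** Two sentences in the SAP would settle it:

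- In 4.5, limit the exclusion of unscheduled post-baseline measurements to descriptive summaries by nominal visit.
- In 6.3, state that the incidence of high, low and clinically significant laboratory values uses all post-baseline values, scheduled and unscheduled, in both numerator and denominator.

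No new data collection or new table is needed. In particular, this does not call for worst-value ECG or vital-sign tables, because SAP 6.3 plans those data as summaries by visit. The cost is a change of input records for existing laboratory tables, and reported abnormality rates that may be slightly higher.
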